#### 16.5 Data and Safety Monitoring:

16.51 The principal investigator(s) and the study statistician will review the study at least twice a year to identify accrual, adverse event, and any endpoint problems that might be developing. The Mayo Clinic Cancer Center (MCCC) Data Safety Monitoring Board (DSMB) is responsible for reviewing accrual and safety data

for this trial at least twice a year, based on reports provided by the MCCC Statistical Office.

16.52 Adverse Event Stopping Rules:

The stopping rules specified below are based on the knowledge available at study development. We note that the Adverse Event Stopping Rule may be adjusted in the event of either (1) the study re-opening to accrual or (2) at any time during the conduct of the trial and in consideration of newly acquired information regarding the adverse event profile of the treatment(s) under investigation. The study team may choose to suspend accrual because of unexpected adverse event profiles that have not crossed the specified rule below.

Phase I: By the nature of the “cohorts of three” phase I study design, toxicity (i.e., adverse events that are possibly, probably or definitely related to study treatment) stopping rules are in place for each dose level. Specifically, if 2 or more dose-limiting toxicities (DLTs) are observed during Cycle 1 at any given dose level, accrual to that dose level will be stopped, and patients will be accrued to the next lower dose level until a maximum of 6 patients are treated at the lower level. Note that a DLT that affects dose escalation is only that which is observed in the first cycle of treatment. However, adverse events for all cycles will be reviewed and the study team will determine whether the dose level needs to be adjusted for future patients. Specifically, if one of the following occurs, then enrollment should stop and the trial should be re-evaluated whether to continue or close the trial permanently to accrual. The study team will evaluate all toxicities on all dose levels before determining how to proceed.

- if  $\geq 1$  in the first 3 patients experience a Grade 4 or higher non-hematologic adverse event at least possibly related to treatment over all cycles at any dose level
- $\geq 2$  in the first 6 patients experience a Grade 4 or higher non-hematologic adverse event at least possibly related to treatment over all cycles at any dose level

Phase II: Accrual will be temporarily suspended to this study if at any time we observe events considered at least possibly related to study treatment (i.e. an adverse event with attribute specified as “possible,” “probable,” or “definite”) that satisfy one of the following:

- if 5 or more patients in the first 15 treated patients experience a Grade 4 or higher non-hematologic adverse event at least possibly related to treatment.
- if after the first 15 patients have been treated, 30% of all patients experience a Grade 4 or higher non-hematologic adverse event at least possibly related to treatment.

We note that we will review Grade 4 and 5 adverse events deemed “unrelated” or “unlikely to be related”, to verify their attribution and to monitor the emergence of a previously unrecognized treatment-related adverse event.

16.6 Results Reporting on ClinicalTrials.gov

At study activation, this study will have been registered within the “ClinicalTrials.gov” website. The Primary and Secondary Endpoints along with other required information for this study will be reported on [www.ClinicalTrials.gov](http://www.ClinicalTrials.gov). For purposes of timing of the Results Reporting, the initial estimated completion date for the Primary Endpoint of this study is 3.5 years after the study opens to accrual. The definition of “Primary Endpoint

Completion Date" (PECD) for this study is at the time the last patient registered has been followed for at least 6 months.

16.7 Inclusion of Women and Minorities:

16.71 This study will be available to all eligible patients, regardless of race, gender, or ethnic origin.

16.72 There is no information currently available regarding differential effects of this regimen in subsets defined by race, gender, or ethnicity, and there is no reason to expect such differences to exist. Therefore, although the planned analysis will, as always, look for differences in treatment effect based on racial and gender groupings, the sample size is not increased in order to provide additional power for subset analyses.

16.73 The geographical region served by MCCC has a population which includes approximately 3% minorities. Based on prior MCCC studies involving similar disease sites, we expect about 3-5% of patients will be classified as minorities by race and about 33% of patients will be women. Expected sizes of racial by gender subsets are shown in the following table:

**Accrual Estimates by Gender/Ethnicity/Race**

Ethnic Category	Accrual Targets		
	Sex/Gender		
	Females	Males	Total
Hispanic or Latino	0	1	1
Not Hispanic or Latino	21	41	62
Ethnic Category: Total of all subjects	21	42	63
Racial Category			
American Indian or Alaskan Native	0	0	0
Asian	0	0	0
Black or African American	1	1	2
Native Hawaiian or other Pacific Islander	0	0	0
White	20	41	61
Racial Category: Total of all subjects	21	42	63

**Ethnic Categories:** **Hispanic or Latino** – a person of Cuban, Mexican, Puerto Rican, South or Central American, or other Spanish culture or origin, regardless of race. The term "Spanish origin" can also be used in addition to "Hispanic or Latino."  
**Not Hispanic or Latino**

Racial Categories:	American Indian or Alaskan Native – a person having origins in any of the original peoples of North, Central, or South America, and who maintains tribal affiliations or community attachment.
	Asian – a person having origins in any of the original peoples of the Far East, Southeast Asia, or the Indian subcontinent including, for example, Cambodia, China, India, Japan, Korea, Malaysia, Pakistan, the Philippine Islands, Thailand, and Vietnam. (Note: Individuals from the Philippine Islands have been recorded as Pacific Islanders in previous data collection strategies.)
	Black or African American – a person having origins in any of the black racial groups of Africa. Terms such as “Haitian” or “Negro” can be used in addition to “Black or African American.”
	Native Hawaiian or other Pacific Islander – a person having origins in any of the original peoples of Hawaii, Guam, Samoa, or other Pacific Islands.
	White – a person having origins in any of the original peoples of Europe, the Middle East, or North Africa.

#### 17.0 Pathology Considerations/Tissue Biospecimens: None.

## 18.0 Records and Data Collection Procedures

### 18.1 Submission Timetable

Data submission instructions for this study can be found in the Case Report Form packet.

### 18.2 Event monitoring

See [Section 4.2](#) and data submission table in the case report form packet for the event monitoring schedule.

### 18.3 CRF completion

This study will use Medidata Rave for remote data capture (rdc) of all study data.

### 18.4 Site responsibilities

Each site will be responsible for insuring that all materials contain the patient's initials, MCCC registration number, and MCCC protocol number. Patient's name must be removed.

### 18.5 Supporting documentation

This study requires supporting documentation for diagnosis prior to study entry as well as for evidence of response to study therapy and progression after study therapy. Supporting documentation for diagnosis will include either a pathology report or a laboratory report demonstrating multiple myeloma (including SPEP, UPEP, FLC, Serum and Urine Immunofixation, Bone Marrow Biopsy and Aspirate, skeletal bone survey, PET scan, Plasma Cell Proliferation and Assessment and FISH). These reports should be uploaded into the Supporting Documentation: Baseline form within 14 days of registration.

For progression of disease prior to study entry, supporting documentation includes the evidence needed to determine the patient's progression prior to enrollment. These documents should be uploaded into the Supporting Documentation: Baseline form within 14 days of registration.

For response to treatment, supporting documentation may include SPEP, UPEP, FLC, Serum and Urine Immunofixation, Bone Marrow Biopsy and aspirate, skeletal bone survey, and PET scan. These documents should be uploaded into the Supporting Documentation form.

For patients who progress after study therapy supporting documentation may include any of the following: SPEP, UPEP, FLC, serum and urine immunofixation, bone marrow biopsy and aspirate, skeletal bone survey, and PET scan. These documents should be uploaded into the Supporting Documentation form.

### 18.6 Labelling of materials

Each site will be responsible for insuring that all materials contain the patient's initials, MCCC registration number, and MCCC protocol number. Patient's name must be removed.

### 18.7 Incomplete materials

Any materials deemed incomplete by the MCCC Operations Office will be considered "not received" and will not be edited or otherwise processed until the missing

information is received. A list of the missing documents will be made available to the appropriate co-sponsor/participant.

18.8 Overdue lists

A list of overdue materials and forms for study patients will be generated monthly. The listings will be sorted by location and will include the patient study registration number. The appropriate co-sponsor/participant will be responsible to obtain the overdue material.

**19.0 Budget**

- 19.1 Costs charged to patient: All routine clinical care. Ibrutinib will be provided free of charge by Pharmacyclics (an AbbVie company).
- 19.2 Tests to be research funded: Correlative studies outlined in Sections 14.0.
- 19.3 Other budget concerns: Protocol administration, study coordinator time, data management, and statistical analysis efforts will be funded by Pharmacyclics (an AbbVie company).

### Appendix I Myeloma Frailty Score

Variable	Patient Category	Score
Age	$\leq 75$ years	0
	76-80 years	1
	$>80$ years	2
Charlson Index (See Appendix III)	Charlson $\leq 1$	0
	Charlson $\geq 2$	1
Activities of Daily Living (ADL) Score (See Appendix II)	ADL $> 4$	0
	ADL $\leq 4$	1
Instrumental Activities of Daily Living (IADL) Score (see Appendix II)	IADL $> 5$	0
	IADL $\leq 5$	1

Additive Total Score	Patient Status
0	Fit
1	Intermediate fitness
$\geq 2$	Frail

## Appendix II Activities of Daily Living (ADL) and Instrumental Activities of Daily Living (IADL)

Score	ADL	IADL
0-1	Bathing (tub bath, shower, sponge bath)	Ability to use the telephone
0-1	Dressing (taking clothes from the wardrobe/drawers and getting dressed)	Shopping
0-1	Toileting (going to the toilet room, using toilet, arranging clothes)	Food preparation
0-1	Transferring	Housekeeping
0-1	Continence	Laundry
0-1	Feeding	Mode of transportation
0-1	-	Responsibility for own medications
0-1	-	Ability to handle finances

For each category, the patient receives a score of 1 if they can complete the activity and a score of 0 if they cannot complete the activity. The sum of each column is computed to get total scores for ADL and IADL.

### Appendix III Charlson Comorbidity Index

[http://www.uroweb.org/fileadmin/livesurgery/Charlson\\_Comorbidity\\_Index.pdf](http://www.uroweb.org/fileadmin/livesurgery/Charlson_Comorbidity_Index.pdf)

*AKA: Charlson Comorbidity Index, Comorbidity-Adjusted Life Expectancy*

1. Indication
  1. Assess whether a patient will live long enough to benefit from a specific screening measure or medical intervention
2. Scoring: Comorbidity Component (Apply 1 point to each unless otherwise noted)
  1. Myocardial Infarction
  2. Congestive Heart Failure
  3. Peripheral Vascular Disease
  4. Cerebrovascular Disease
  5. Dementia
  6. COPD
  7. Connective Tissue Disease
  8. Peptic Ulcer Disease
  9. Diabetes Mellitus (1 point uncomplicated, 2 points if end-organ damage)
  10. Moderate to Severe Chronic Kidney Disease (2 points)
  11. Hemiplegia (2 points)
  12. Leukemia (2 points)
  13. Malignant Lymphoma (2 points)
  14. Solid Tumor (2 points, 6 points if metastatic)
  15. Liver Disease (1 point mild, 3 points if moderate to severe)
  16. AIDS (6 points)
3. Scoring: Age
  1. Age <40 years: 0 points
  2. Age 41-50 years: 1 points
  3. Age 51-60 years: 2 points
  4. Age 61-70 years: 3 points
  5. Age 71-80 years: 4 points
4. Interpretation
  1. Calculate Charlson Score or Index (i)
    1. Add Comorbidity score to age score
    2. Total denoted as 'i' below
  2. Calculate Charlson Probability (10 year mortality)
    1. Calculate  $Y = e^{(i * 0.9)}$
    2. Calculate  $Z = 0.983^Y$
    3. where Z is the 10 year survival
5. References
  1. Charlson (1987) J Chron Dis 40: 373-83
  2. Gold (1994) J Clin Epidemiol 47: 1245-51

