### 1.2 Treatment for Multiple Myeloma

Treatment choices for multiple myeloma vary with age, performance status, comorbidity, the aggressiveness of the disease, and related prognostic factors. Newly diagnosed patients with multiple myeloma are typically categorized into 2 subpopulations usually defined by their age and suitability for the subsequent approach to treatment. Younger patients will typically receive an induction regimen followed by consolidation treatment with high-dose chemotherapy and autologous stem cell transplantation (ASCT). For those not considered suitable for high-dose chemotherapy and ASCT, longer-term treatment with multi-agent combinations including alkylators, high-dose steroids, and novel agents are currently considered as standards of care.

Over the past few years several novel treatments (immunomodulatory drugs; IMiDs and proteasome inhibitors) have become available for patients with MM. Although higher percentages of patients are achieving remission, all patients eventually relapse and become resistant to therapy. Novel agents and new combinations regimens are needed for improved outcome in this disease. There is an increasing body of evidence suggesting that clinical or laboratory parameters may be important in selecting specific treatment options for patients with MM. This is further important since the novel agents being used for the treatment of MM have their own inherent side effect profiles that are unique and need specific management as against the more expected adverse events from conventional chemotherapeutic agents. This is especially true in elderly patients who may

have other comorbidities, since the median age at diagnosis for MM is 70 years. Thus, there is a constant need to develop newer, better tolerated agents/regimens that can keep the disease controlled for prolonged durations as well as be safe with respect to low cumulative toxicities. A recently developed tool based on geriatric assessment has been validated in a pooled analysis by the International Myeloma Working Group and is recommended to be used prospectively in trials focusing on non-transplant eligible newly diagnosed MM patients, which is the target population for this proposed clinical trial. This tool will be utilized in the said protocol to address patient eligibility.

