#### 3.1 Inclusion Criteria

3.11 Age  $\geq$ 18 years.

3.12 Diagnosis:

3.121 Phase I: Confirmed diagnosis of relapsed or refractory multiple myeloma

3.122 Phase II: Confirmed diagnosis of active multiple myeloma and must be newly diagnosed.

**NOTE:** All tests for establishing disease status must be completed  $\leq$ 28 days prior to registration.

3.13 Measurable disease  $\leq$ 28 days prior to registration, defined by at least one of the following:

- Serum monoclonal protein  $\geq$ 1.0 g/dL (see Section 11.1 for definition)
- $>200$  mg of monoclonal protein in the urine on 24-hour electrophoresis
- Serum immunoglobulin free light chain  $>10$  mg/dL AND abnormal serum immunoglobulin kappa to lambda free light chain ratio.
- Monoclonal bone marrow plasmacytosis  $>30\%$  (evaluable disease).

3.14 Prior treatment:

3.141 Phase I: Exposure to 2-3 prior lines of therapy or no therapeutic options

3.142 Phase II: Previously untreated for symptomatic MM.

**EXCEPTION:**  $\leq$ 7 days with pulse steroids or localized radiation therapy, without curative intent, for a myeloma-related complication prior to registration is allowed, as considered necessary by the treating physician.

3.15 Myeloma Frailty Score:

**NOTE:** This will include calculating a frailty score [[Appendix I](#); based on age, activities of daily living, instrumental activities of daily living ([Appendix II](#)) and Charlson comorbidity index ([Appendix III](#))].

3.151 Phase I: “Intermediate fitness” or “Frail”

**NOTE:** No “fit” patients will be included in the phase 1 portion of the trial which is being done to determine the MTD of the 3-drug combination.

3.152 Phase II: Transplant-ineligible as per their treating physician.

**NOTE:** All the patients with “intermediate fitness” or “frail” status will be considered transplant-ineligible. Other reasons to consider transplant ineligibility may include, but are not limited to: financial constraints or patient preference. In case such patients have a frailty score of “fit”, it should be duly noted by the treating physician.

3.16 ECOG Performance Status 0, 1, or 2 ([Appendix IV](#)).

3.17 The following laboratory values obtained  $\leq$ 14 days prior to registration:

- Absolute neutrophil count (ANC)  $\geq$ 1,000 cell/mm^3 without growth factor support

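### The frailty score scores age separately but takes its Charlson point from an index that already contains age points, so as written nobody over 50 can be Fit and the phase I exclusion of fit patients removes nobody over 50

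*Combined protocol and SAP*

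**What the plan says.** Section 1.2 describes a validated geriatric assessment tool and says of it: "This tool will be utilized in the said protocol to address patient eligibility". The 3.15 note says the score is "based on age, activities of daily living, instrumental activities of daily living" and the Charlson comorbidity index, so age and Charlson are separate inputs.

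Appendix I adds four items:

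- age: 0 up to 75, 1 at 76-80, 2 above 80
- Charlson, labelled "Charlson Index (See Appendix III": 0 if at most 1, 1 if 2 or more
- ADL: 1 if 4 or less
- IADL: 1 if 5 or less

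A total of 0 is Fit, 1 is Intermediate fitness, and 2 or more is Frail.

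Appendix III lists comorbidities under item 2, headed "Scoring: Comorbidity Component (Apply 1 point to each unless otherwise noted". Item 3 then gives points for age, among them "Age 51-60 years: 2 points", with 1 at 41-50, 3 at 61-70 and 4 at 71-80. Item 4 defines the Charlson score or index: "Add Comorbidity score to age score".

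The category is used in three places. Section 3.151 admits only Intermediate or Frail patients to phase I. Section 3.152 leaves phase II transplant ineligibility to the treating physician, counts all Intermediate and Frail patients as ineligible for transplant, and asks the physician to note any fit entrant. Section 12.3 records the category as a descriptive factor.

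**The concern.** The two appendices do not fit together. Appendix I allows age to contribute nothing until 76. The index it points to lets age alone cross the Charlson cut-off from 51, which defeats the 0 points up to 75. Section 1.2 states that "the median age at diagnosis for MM is 70 years", so the affected range is where many patients with this disease would be expected to lie.

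The consequence is in phase I, where the category decides entry. If the literal rule is followed, the exclusion of fit patients from the cohorts that determine the MTD has no effect above age 50. If some readers stop at item 2 of Appendix III and others continue to item 4, the same patient can be admitted by one and refused by another.

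In phase II the stake is smaller: the automatic transplant-ineligible label, the physician's note for fit entrants, and the 12.3 category used to describe the population.

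**Working it through.** The plan states no figure to reproduce here, so the check applies the scoring rules as printed, under both readings.

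**Rule.** Frailty total = age item + (1 if Charlson ≥ 2) + (1 if ADL ≤ 4) + (1 if IADL ≤ 5).

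- Literal reading: Charlson = comorbidity points + Appendix III age points.
- Comorbidity-only reading: Charlson = comorbidity points.

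**Gaps in Appendix III.** It has no band for exactly 40 or above 80. Age 40 is given 0 age points. Above 80 the choice does not matter, because Appendix I already gives 2 points (Frail).

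**One case.** Age 70, no comorbidity, ADL 6 and IADL 8. Appendix II has 6 ADL and 8 IADL items, and "The sum of each column is computed to get total scores for ADL and IADL", so these are the maxima.

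- Literal: Charlson = 0 + 3 = 3, so the total is 0 + 1 + 0 + 0 = 1. Intermediate; meets 3.151.
- Comorbidity-only: Charlson = 0, so the total is 0 + 0 + 0 + 0 = 0. Fit; fails 3.151.

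**All ages, ADL > 4 and IADL > 5.** The bands are those at which either appendix changes. Each cell gives the category with 0 / 1 / 2 or more comorbidity points.

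| Age | Literal | Comorbidity-only |
|---|---|---|
| 18-40 | Fit / Fit / Int. | Fit / Fit / Int. |
| 41-50 | Fit / Int. / Int. | Fit / Fit / Int. |
| 51-60 | Int. / Int. / Int. | Fit / Fit / Int. |
| 61-70 | Int. / Int. / Int. | Fit / Fit / Int. |
| 71-75 | Int. / Int. / Int. | Fit / Fit / Int. |
| 76-80 | Frail / Frail / Frail | Int. / Int. / Frail |
| over 80 | Frail / Frail / Frail | Frail / Frail / Frail |

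That is 7 bands × 3 = 21 profiles.

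- Fit, comorbidity-only: 5 bands × 2 = 10.
- Fit, literal: 2 + 1 = 3.
- Difference: 10 − 3 = 7, made up of 41-50 with exactly 1 comorbidity point (1), and 51-60, 61-70 and 71-75 with 0 or 1 (3 × 2 = 6).

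Enumerating every whole-year age from 18 to 100 gives the same limits: Fit is attainable at 18-50 on the literal reading and at 18-75 on the other, that is, at none against 25 of the ages above 50.

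**Other shifts.** The 7 profiles above that score an ADL point only, or an IADL point only, move from Intermediate to Frail (7 × 2 = 14). So do ages 76-80 with 0 or 1 comorbidity points and no ADL or IADL point (2). These 14 + 2 = 16 moves change eligibility in neither phase, because both categories are treated alike.

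**The case against.** The strongest reply is that nobody would score it literally. Appendix III is a general-purpose sheet whose stated use is judging life expectancy, and items 3 and 4 lead to a 10-year survival formula that this protocol does not use. Section 3.15 lists age separately, and item 2 has its own comorbidity heading, so a clinician could reasonably take that component and stop. This makes the literal outcome less likely in practice, but it does not settle the text. Appendix I names the Charlson index, and only item 4 defines one. The eligibility checklist might settle the scoring, but it is not in the documents.

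One can also say that the literal rule gives every patient a definite category, and that counting age twice in a composite is odd but not contradictory. That is fair as far as it goes: the validated tool is not reproduced here, so the documents alone cannot prove which version was intended. The rule nevertheless overrides Appendix I's own 0 points up to 75 and empties an eligibility criterion above age 50.

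The profile counts are a weak measure, and this stands. They depend on the banding. Over whole-year ages 18-75 (58 ages) with 0 or 1 comorbidity points, the literal rule keeps 23 × 2 + 10 × 1 = 56 of 58 × 2 = 116 combinations as Fit, or 48%, against 3 of 10 (30%) by bands. Neither is weighted to patients. The age limits and the age-70 case carry the point.

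It also stands that fit patients may enter phase II, that section 16 plans no analysis by frailty, and that no effect on the MTD can be shown.

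**Conclusion.** The concern holds. Read as written, the oldest age at which a patient can be Fit is 50; with comorbidity points only it is 75. The 3.151 exclusion therefore removes nobody over 50 on the literal reading. Phase I eligibility turns on the reading at ages 51-75 with 0 or 1 comorbidity points, and at 41-50 with exactly 1, when ADL and IADL score no points.

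The result does not depend on how the missing band above 80 is filled. It does not show how sites scored, how many patients were affected, or any effect on the MTD; the documents give none of these. Phase II eligibility is unaffected because it rests on the treating physician, and no error rate, sample size or planned analysis in section 16 changes. The mismatch should be corrected, but it is an eligibility and description problem and leaves the phase II test intact.

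**What to change.** Reconcile Appendices I and III. State in Appendix I which Charlson total feeds the frailty score, after checking the validated tool cited in section 1.2. The comorbidity component alone (Appendix III, item 2) is the reading that fits a separate age item; if the check confirms it, mark items 3 and 4 as not used for the frailty score.

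Optionally, where item-level comorbidities were recorded, re-derive the 12.3 category and report how many phase I patients would have been Fit.

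The amendment is a sentence or two. The re-derivation depends on item-level data that the documents do not show were collected. If comorbidity-only is confirmed, some patients who are Intermediate under the literal rule become Fit; they would be ineligible for phase I and would need the physician's note in phase II.
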